

Statistical considerations
	
Sample size calculation Assuming 20% change, a sample size of 91 per group is required to detect a change from 30 to 50% in primary outcomes based on $\alpha = 0.05$, $1-\beta = 0.8$. Assuming a design effect due to clustering of 2, a total sample of 360 is required (180 in each group).
 
Analysis plan For analysis of differences between the intervention and usual care alternatives, linear or generalised multi-level mixed models will be estimated depending on the type of outcome in question. Intra-class correlations will be calculated to compare the amount of variance associated with design features as individual participants are nested within care coordinators who are nested within community mental health teams, and those same participants are also nested within GPs who may also be nested within medical centres, which will occur before selecting random effects for these models. As well as an analysis of completers, defined as those consumers, care coordinators and GP triads that complete an online shared care plan, an intention to treat (ITT) analysis will also be completed for this study. For the ITT analysis, those who have dropped out will be treated using a variety of sensitivity analyses. Further, baseline predictors and intervention features of both the SHAReD (e-shared care) and usual care situations will be added to multi-level models to identify effects of these characteristics on outcomes. Qualitative analyses (predominantly deductive but inductive coding will also be applied to detect new and emerging themes) will also be undertaken. All relevant costs such as implementation costs and healthcare usage [hospitalisations, GP care, specialists, allied health, and prescribed medication, and the multiple outcomes such as interactions with the health system, engagement, preventive tests undertaken, clinical measures and quality of life for participants in the intervention and usual care groups will be quantified, and tests of significance will be undertaken on these data. These results will be used in a cost-consequence analysis (CCA). A comprehensive within-trial cost-effectiveness study will also be conducted provided effectiveness has been demonstrated, with the main effects/benefits consisting of satisfactory completion of an online shared care plan, reduction in consumer cardiometabolic risk, and avoiding unplanned hospitalisations. A cost-utility evaluation will be conducted if effectiveness in relation to quality of life has been demonstrated, to provide a ranking of the alternatives (e-shared care, usual care) on the basis of the amount of resources (costs) used to gain an extra quality adjusted life year (QALY) by receiving the SHAReD intervention. All the necessary effects/benefits and costs (direct medical, consumer costs for medical care and any indirect costs) will be identified, counted and valued using established methods. A range of incremental cost-effectiveness ratios (ICERs) will be calculated such as the incremental cost for an extra QALY gained, cost for an unplanned hospitalisation that was avoided. Sensitivity analysis will be conducted and some results presentations graphically.

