4. STUDY DESIGN

4.1. DESIGN / STUDY TYPE

This is a pragmatic cluster randomised controlled trial. The unit of randomisation is the team. The teams are four of the five Adult Community Mental Health 'Core' Teams in SLHD (Table 1). Randomisation will be stratified by sector (Eastern and Western): One team from each sector will be randomised to the intervention group, the other team will be allocated to the comparison group. The comparison group Teams will receive the intervention after the 3-month data collection is complete.

As there are only two teams per sector in the study, randomisation will be done by a person independent from the study by flipping a coin.

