8.2. PROVIDE A DETAILED ANALYSIS PLAN

Quantitative analysis

The fidelity and tailoring of the intervention to participants' needs will be assessed by analysing records, provider and consumer interviews 3 months after their usual shared care appointments. We will compare outcomes over 3 months after intervention between SHAReD intervention and comparison groups with linear or generalised multi-level mixed models including age, sex and key independent variables that are found to be significantly different between groups at baseline. Intra-class correlations will be calculated to compare the amount of variance associated with design features such as individual participants nested within care coordinators who are nested within community mental health teams, and those same participants are also nested within GPs who could also be nested within medical centres, before selecting random effects for these statistical models. As well as an analysis of completers (defined as those consumers, care coordinator and GP who

consented and are engaged in shared care), an intention to treat (ITT) analysis will also be included for this project. For the ITT analysis, those who drop out of the study (defined as consumers who were discharged of shared care or who withdrew consent) will be treated using a variety of sensitivity analyses including multiple imputation for the missing values on key measures resulting from them dropping out of the study. Sensitivity analyses will assess unmeasured variation.

Qualitative analyses

This will evaluate the experience of participants, carers and providers, barriers to implementation, conditions for sustainability and translation. Qualitative data will be managed and coded using NVivo 11 analysis software (QSR International). Two researchers will review each transcript and develop coding aligned with the Theoretical Domains Framework and Normalisation Process Theory.^{25,26} Coding will be predominantly deductive but inductive coding will also be applied to detect new and emerging themes.

Data combining and cost analyses

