Secondary data from GP records, and SLHD eMR data (including hospitalisations, ED visits and ambulatory care records, associated costs, documentation audit report and metabolic report) as well as information from SLHD Targeted Activity & Reporting System (STARS) will be obtained and merged with the consumer survey data within the SLHD by AI [name]/AI [name]. GP records will be used to answer research questions 1 and 2 – quantitative analysis is described above. SLHD's patient data from the eMR (including hospitalisation, ED visits, ambulatory data, documentation audit and metabolic monitoring) as well as information from STARS and cost information will be used to answer research questions 3 and 4. These analyses of the resulting combined and de-identified dataset are described below.

The merged SLHD administrative data (micro-level data) will be from a 6-month period post-intervention (May-October 2023, considering the intervention as having a shared care plan in Inca between May and June 2023) compared with the 6-month periods, a) pre-intervention (November 2022-April 2023) and b) in the previous year (May-October 2022, to check for seasonal effect). The data will be analysed as part of the healthcare cost component (in the larger health economic evaluation).

The healthcare usage (such as hospitalisations, ED visits, ambulatory care and GP care) data will firstly be grouped in a meaningful way e.g., for hospitalisations, summarised by ARDRGs, diagnoses and average length of stay. Costs will be summarised too e.g., for hospitalisation costs, these will be described in terms of main components such as 'Medical', 'Nursing' and 'Allied Health' costs occurring during admissions. We will calculate the total and mean utilisation of healthcare services and costs (and undertake further econometric analyses) for those in the SHAReD intervention, usual care, and combined (SHAReD and comparison) groups. These summary statistics (and later modelled estimates) will be included in the cost component of the economic evaluation.

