Additionally, it will be informative to measure the healthcare costs of SMI from the viewpoint of the SLHD/NSW health system, expressed as average total costs of SMI treatment per person under the alternative care situations. The SHAReD care group may be broken down into several subgroups for the analysis, and based on the degree to which they completed the intervention (e.g. their adherence to the shared e-plan, how many times they were engaged with the essential components

of the intervention and what they received, the quality of SHAReD care delivery, and participant acceptability and responsiveness to the intervention).²⁷ All costs will be expressed in 2023 Australian dollars.

Econometric methods commonly used to address issues associated with healthcare usage and cost variables such as problems of heteroscedasticity and skewness will be applied in this study.²⁸ These methods will be used to estimate the total (and differences in/incremental) costs (and costs specific to single and multiple health conditions, health risks, cardiometabolic outcomes) associated with the SHAReD care situation versus usual care adjusted for several participant and system-level characteristics. Various econometric methods will be explored such as log-transformed ordinary least squares models, GLMs (and may be those for repeated measures/panel data too) and survival (duration) models, with “goodness of fit” and other statistical measures used to make decisions about the models.²⁹

There may be missing data especially from the survey or general practice or as a result of merging data. This will be addressed by multiple imputation in the analysis.

To address confounding, variables with baseline differences between SHAReD intervention and usual care will be included in the final multivariate regression analysis.

To manage any risk that merging databases of non-identifiable data could subsequently result in the individuals being identified, data will be de-identified after combining the SLHD eMR data and costs with consumer survey data and stored securely (see section 12 of protocol). Only data with more than five individual responses will be released.

Costing component and the economic evaluation

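### The synopsis reads coefficients of post-allocation intervention features as effects on outcomes; they are confounded by engagement and should be fitted separately and reported as exploratory associations

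*Protocol*

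**What the plan says.** The analysis plan under Statistical considerations in the protocol synopsis goes in this order.

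- It starts with the between-arm comparison: "For analysis of differences between the intervention and usual care alternatives, linear or generalised multi-level mixed models will be estimated".
- It then plans a completer analysis and states that "an intention to treat (ITT) analysis will also be completed for this study".
- As a further step, which also covers predictors measured at baseline, it says: "intervention features of both the SHAReD (e-shared care) and usual care situations will be added to multi-level models to identify effects", meaning effects on the trial outcomes.

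That last sentence does not define the features. It treats them in the same way as baseline predictors, does not call the analysis exploratory, and names no causal method such as mediation or instrumental variables.

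Section 8.2 (Quantitative analysis) describes the arm comparison with models "including age, sex and key independent variables that are found to be significantly different between groups at baseline". It lists no intervention feature and does not repeat the synopsis sentence.

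The nearest description of such features is in the cost part of section 8.2, where the intervention group may be split by, among other things, "their adherence to the shared e-plan, how many times they were engaged with the essential components" of the intervention, together with delivery quality and acceptability.

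**The concern.** A baseline predictor is fixed before allocation and can enter an outcome model safely. A feature of the care received cannot be treated in the same way. Consumers who are in contact with their GP, and GPs who are willing to use the software, are more likely to show the feature. They are also more likely to have risks recorded, medication prescribed and advice given, and these are the primary outcomes. A feature that does nothing will then look useful.

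The wording of the plan goes beyond association: it says the models will identify effects. If it is followed as written, the trial could report that a component of the online plan works when the coefficient only shows who was engaged.

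**Working it through.** **1. Are the features set after allocation?** Section 4.1 states: "The unit of randomisation is the team". Section 8.2 dates the intervention by "considering the intervention as having a shared care plan in Inca between May and June 2023". Adherence, number of engagements, delivery quality and acceptability can be observed only after that point. The protocol also shows that exposure depends on the GP and the consumer. Under section 5.3, patients of GPs who decline get no access to the online tool. The synopsis and section 4.5 provide for consumers who have no shared care appointment after baseline.

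**2. How large could the false feature effect be?** The protocol gives no figure on this point, so the size has to be illustrated.

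Inputs:
- From the protocol: 400 consumers expected at follow-up (section 4.2), so 400 / 2 = 200 per arm; outcome rates in the range 30% to 50% (the sample size assumption).
- Assumed: an unmeasured engagement score U, standard normal, that raises the log-odds of the feature by 1 per SD and of the outcome by 0.5 to 1 per SD; no effect of arm or feature; clustering ignored; 800 simulated trials per setting.

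Models:
- Feature: logit P(F = 1) = a(arm) + 1 × U
- Outcome: logit P(Y = 1) = c + b × U, with b = 0.5 or 1
- Fitted with the feature: logit P(Y = 1) = β0 + β1 × arm + β2 × F
- Fitted without it: logit P(Y = 1) = β0 + β1 × arm

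The true values of β1 and β2 are zero, so each odds ratio (OR) should be 1.0 and be significant in 5% of trials. Results as b goes from 0.5 to 1:

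| Feature frequency, usual care / intervention | Feature OR | Feature falsely significant | Arm OR in the same model |
|---|---|---|---|
| 0% / 50% | about 1.5 to 2.1 | about 25% to 70% | about 0.8 to 0.7 |
| 30% / 60% | about 1.5 to 2.0 | about 45% to 95% | about 0.9 to 0.8 |
| 40% / 50% | about 1.5 to 2.0 | about 45% to 95% | about 0.97 to 0.94 |
| 50% / 50% | about 1.5 to 2.0 | about 40% to 95% | about 1.0 |

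Without the feature in the model, the arm OR is about 1.00 and about 5% of trials reject.

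**3. What decides the shift in the arm coefficient?** In a linear model, the arm coefficient with the feature equals the coefficient without it minus γ × (q1 − q0). Here γ is the feature coefficient, and q1 and q0 are the feature frequencies in the intervention and usual care arms. A second simulation used a linear probability model with 400,000 consumers, a 30% control rate, a true arm effect of 0.20, no feature effect, and engagement worth 0.10 per SD:

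- Feature in 0% / 60%: γ = 0.082 and the arm coefficient falls from 0.197 to 0.150. The shift is 0.047, and 0.047 / 0.082 = 0.57.
- Feature in 30% / 60%: γ = 0.083 and the arm coefficient falls from 0.202 to 0.182. The shift is 0.020, and 0.020 / 0.083 = 0.24.
- Feature in 50% / 50%: γ = 0.085 and the arm coefficient stays at 0.199.

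The quotients are the realised gaps in frequency. They are slightly below the nominal 0.6 and 0.3 because the nominal frequencies apply at average engagement. With engagement worth 0.05 to 0.15 per SD, the false feature effect runs from about 0.04 to 0.13. If the feature is unrelated to engagement, it is about zero (−0.002 to 0.001) and the arm coefficient does not move.

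So the false feature effect needs only shared dependence on engagement. A shift in the arm coefficient also needs a difference in feature frequency between arms.

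**The case against.** The strongest reply is that the arm effect is already protected. The feature sentence comes as an additional step after the arm comparison and the intention-to-treat analysis, and has its own purpose. Section 8.2 lists only age, sex and baseline-imbalanced variables for the arm comparison. This stands. A reader might infer that the trial's treatment effect is biased, but the documents do not say that it will be read from the extended model. Nor does the largest shift in the table represent the plan: it needs a feature that never occurs in usual care, whereas the sentence covers features of both care situations.

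A second reply is that the features are undefined and could include delivery variants. Section 6.2, for example, lets either the GP or mental health staff create the plan, depending on GP workload. Confounding by consumer engagement is less obvious there, and the list of features can be left to a statistical analysis plan. This also stands, and it is why the size is only illustrative. It does not cover the claim to identify effects, which the protocol itself makes.

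Two further readings are tempting but unsupported. Section 8.2 says that "The fidelity and tailoring of the intervention to participants' needs will be assessed by analysing records" and interviews, but it does not put fidelity into an outcome model. And no passage makes roll-out, or the choice of components to keep, depend on these coefficients; section 1.2 ties roll-out only to the success of the intervention.

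**Conclusion.** The point holds for the feature coefficients. As worded, the synopsis would present confounded associations of post-allocation features as effects. Under the assumed engagement strengths, a feature with no effect shows an odds ratio of about 1.5 to 2.1 and is falsely significant in roughly 25% to 95% of trials, depending on engagement strength and on how often the feature occurs in each arm.

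The intention-to-treat comparison, the arm model in section 8.2 and the baseline predictors are not affected. An arm coefficient taken from the further model would lie at about 0.7 to 1.0 on the odds ratio scale when the truth is 1.0, with no shift when the feature is equally common in both arms.

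These figures rest on assumed engagement effects and ignore clustering. The existence of the problem rests only on the timing of the features and their plausible dependence on engagement.

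**What to change.** In the synopsis analysis plan:

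1. Split the sentence so that baseline predictors and post-allocation features are handled separately.
2. State that the arm effect is taken only from the model with arm, design terms and baseline covariates, as section 8.2 already implies.
3. Fit the feature analyses separately, within arm and adjusted for baseline values.
4. Replace the wording about identifying effects with wording about exploring associations, and label the results exploratory. Adjustment for baseline values reduces confounding by engagement but does not remove it, so the label is needed in any case.

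The change is to wording only: no new data and no change in sample size. The sponsor gives up causal statements about individual components.

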1. BACKGROUND AND INTRODUCTION

1.1. DISEASE/PROPOSED INTERVENTION BACKGROUND

The problem

People with severe mental illness (PWSMI) have a 13-30-year shorter life expectancy than the general population.¹⁻³ This is largely attributed to high rates of modifiable cardiometabolic risk factors such as smoking, hyperlipidaemia, hypertension, obesity, diet and sedentary lifestyle,^{4,5} which translates to high rates of chronic disease. As a result, PWSMI are six times more likely to die of cardiovascular disease and four times more likely to die of respiratory disease than the general public.⁶ The annual economic cost of premature comorbidity in this population necessitates better integrated care; primary care is considered ideal for managing multimorbidity.^{7,8} PWSMI have poor uptake of preventive care and proactive use of primary care due to a number of provider issues (e.g. stigma, poor communication) and consumer issues (e.g. cognitive difficulties, low health literacy).⁹ The higher mortality rate among PWSMI also requires urgent attention. The costs of treating PWSMI and premature death among people of PWSMI in Australia in 2016 was \$15 billion.¹⁰

The intervention

An online shared care plan will facilitate coordinated and planned care of consumers of mental health services “consumers” including management of risk factors and referral to allied health services and other relevant programs. It will be adapted from one used for consumers with long-term cancer patients in St George and the existing Mental Health Shared Care Checklist used in the SLHD Living Well Living Longer (LWLL program).¹¹ It will be based on the existing shared care plan used by SLHD, which is a paper form. The use of the existing shared care plan ensures the study is testing the difference between paper and online shared care plans rather than differences in the content of the plans. Functional specifications developed in consultation with mental health services (MHSs), general practitioners (GPs) and consumers in SLHD. The online shared care plan a) is interactive so the GP and MHS can review, edit and add to it (the consumer can view it); b) generates automated reminders for GPs, care coordinators and consumers; and c) enables MHSs to monitor completion and evaluate outcomes. The MHS care coordinators and peer support workers will assist the consumers and any nominated carers to access the INCA software and review their plans.

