A within-trial economic evaluation of the SHAReD intervention compared to usual care will be conducted if effectiveness has been demonstrated. The mean costs and health effects/benefits will be used to generate the incremental cost for a one-unit improvement in the health effect of interest (e.g. an extra Quality Adjusted Life Year [QALY]) for the SHAReD group compared to the usual care group. We will assemble several ICERs such as the incremental cost for each care plan completed, the reduction in cases with cardiometabolic risk (and separate risk factors), unplanned hospital admissions avoided, and a gain in QALYs among the SHAReD group compared with the usual care group. The results of the evaluation will be used to determine the within-trial cost-effectiveness (and utility) of the SHAReD intervention i.e. whether it offered value for money.

The results will be shown graphically on a cost-effectiveness plane.³² Thus, the cost-effectiveness plane will show the differences in healthcare costs and health effects/benefits between the SHAReD intervention and usual care groups in two dimensions, with the healthcare costs plotted against health effects/benefits. We will use the bootstrap method, which is a re-sampling method used to estimate basic statistics on a population through sampling the dataset with replacement, to create 10,000 random samples and then use these samples to establish a statistical distribution for the costs and health effects/benefits (means and standard deviations) in the intervention and control groups, as well as to generate confidence intervals for the applicable ICER.³³ Various sensitivity

analyses will be undertaken. We will also generate a cost-effectiveness acceptability curve to summarise the impact of uncertainty on the results of the evaluation, expressed as the main ICER in relation to possible values of the cost-effectiveness threshold.³⁴ Values for thresholds will be determined by considering what is meaningful for the healthcare provider.

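### One main effect in the cost-effectiveness study, completion of an online shared care plan, is out of the comparison arm's reach, so its increment measures uptake and not benefit over usual care

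*Protocol*

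**What the plan says.** The Synopsis (Statistical considerations) makes the within-trial economic study conditional on the intervention first being shown to work, and describes that study as one "with the main effects/benefits consisting of satisfactory completion of an online shared care plan". Two further effects follow in the same sentence: "reduction in consumer cardiometabolic risk, and avoiding unplanned hospitalisations". Online-plan completion is thus the first of three main effects.

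Section 8.2 (costing component and economic evaluation) words the plan-based effect differently: "We will assemble several ICERs such as the incremental cost for each care plan completed". It does not say online. It also lists the completion rate for care plans among the mean effects to be compared between the two groups, and defines the economic comparator as consumers who did not get SHAReD.

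On what usual care is, section 1.1 says the existing SLHD plan is a paper form and that the online plan is based on it: "The use of the existing shared care plan ensures the study is testing the difference between paper and online shared care plans". On timing, section 4.1 says: "The comparison group Teams will receive the intervention after the 3-month data collection is complete".

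**The concern.** An incremental cost-effectiveness ratio needs an effect that both arms could achieve. Completing an online plan is delivery of the intervention itself. A comparison consumer with a fully completed paper plan of the same content counts as a failure on this measure. The difference between arms is then the intervention arm's uptake.

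Three things are at stake:

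- Objective 4 asks whether the intervention is more cost-effective than usual care. A ratio built on this effect cannot contribute to that answer, because usual care is credited with nothing.
- Both the Synopsis and section 8.2 make the cost-effectiveness study conditional on effectiveness having been shown, and neither says on which outcome. An effect that is positive by construction should not be able to meet that condition.
- Section 8.2 draws an acceptability curve for a main ratio that it does not name, and section 1.2 links success to wider roll-out. A ratio that is favourable by design could reach that decision.

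**Working it through.** The protocol states no completion rate, incremental cost or cost per plan, so there is no figure of its own to reproduce. The check is structural, followed by a range under assumed values.

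**Step 1: the comparison arm's value.** Under section 4.1, comparison teams have no online plan during the comparison period. Under section 8.2, the economic comparator is by definition consumers without SHAReD. Online completion there is 0. One small qualification applies. Section 5.3 puts installation for comparison GPs at 3 months after 30 June 2023, about the end of September, while the post-intervention data window in Table 9 and section 8.2 runs to October 2023. A few comparison-arm online plans could fall in the last month.

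**Step 2: the two increments.** Let pI be completion in the intervention arm, pC any-form completion in usual care, and ΔC the incremental cost.

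- Online-plan effect (Synopsis): pI − 0 = pI, giving a ratio ΔC/pI.
- Any-form effect (one reading of section 8.2): pI − pC, giving a ratio ΔC/(pI − pC).
- Inflation of the effect: pI/(pI − pC).

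This takes all completed plans in the intervention arm as online. If some are on paper, for example where the GP declines, any-form completion there is higher and the factor is smaller.

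**Step 3: the range.** All values of pI and pC are assumptions. The only related figure in the protocol is in section 1.1: 512 of 736 active shared-care consumers had a verified annual health check, and 512/736 = 0.696. That is a health check, not a plan completion rate, and serves here only as a high value for pC.

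| pC (assumed) | Factor at the higher pI | Factor at the lower pI |
|---|---|---|
| 0.10 | 1.0/0.9 = 1.11 (pI 1.0) | 0.3/0.2 = 1.50 (pI 0.3) |
| 0.20 | 1.0/0.8 = 1.25 (pI 1.0) | 0.3/0.1 = 3.0 (pI 0.3) |
| 0.30 | 1.0/0.7 = 1.43 (pI 1.0) | 0.4/0.1 = 4.0 (pI 0.4) |
| 0.50 | 1.0/0.5 = 2.0 (pI 1.0) | 0.6/0.1 = 6.0 (pI 0.6) |
| 0.696 | 1.0/0.304 = 3.3 (pI 1.0) | 0.8/0.104 = 7.7 (pI 0.8) |

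The factor grows without bound as pI approaches pC. If pI is at or below pC, the any-form effect is zero or negative while the online measure still shows a gain. For example, with pI = 0.60 and pC = 0.696 the two effects are +0.60 and −0.096.

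**The case against.** The strongest reply is that section 8.2, the detailed section, already uses neutral wording and says completion rates will be compared between groups. The Synopsis names ratios per QALY and per hospitalisation avoided as examples, and none per online plan. On that reading only a wording mismatch remains, and an analysis plan could settle how completion is operationalised. This stands in part: section 8.2 can be read in the acceptable way. But the Synopsis names the online plan as a main effect, the two places define different effects, and nothing in the protocol says which governs.

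A reader might also infer that the cost per plan is understated several-fold. The protocol does not support that:

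- It gives neither completion rate nor the incremental cost, and the factor is below 2 over much of the range.
- The 70% figure is an annual health check among active shared-care consumers, whereas section 5.1 also admits people only willing to start shared care.
- Section 5.3 keeps consumers in follow-up without online access when their GP declines, so high online completion cannot be presumed.
- ΔC/pI is a correct cost per online plan. It is too low only if read as the cost per additional plan of any kind.
- Understatement presumes a positive incremental cost, and hypothesis 4 in section 2 expects costs to be avoided.

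Nor does it follow that objective 4 goes unanswered. The disaggregated cost-consequence analysis and the ratios for cardiometabolic risk, unplanned admissions and QALYs do not depend on this measure. Online-plan completion is also absent from the endpoints in section 4.4 and the outcomes in Table 9, so nothing ties the effectiveness condition to it. The gap is that nothing excludes it either.

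**Conclusion.** The point holds for this one effect measure. As the Synopsis words it, the comparison arm is at essentially zero by design, the increment is intervention uptake, and the resulting ratio cannot show benefit over usual care. The Synopsis and section 8.2 also define the plan-based effect differently. This conclusion rests on the protocol's description of usual care and of when comparison teams receive the software, not on any assumed rate.

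The size is not fixed by the document. Relative to an any-form effect, the inflation runs from about 1.1 (pC 0.10, pI 1.0) to 7.7 (pC 0.696, pI 0.80), and further as pI nears pC. No single multiple can be claimed. The change is worth making because it is cheap and removes a ratio that is favourable by construction.

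**What to change.** - In the Synopsis, replace the online-plan effect with completion of a shared care plan in any form, paper or online, judged by the same criteria in both arms. Use that definition in section 8.2 for both the completion rate and the cost per completed plan.
- Confirm that a source available in both arms captures completed paper plans. The CMH011 Document Audit and GP records are candidates, but the protocol does not say that either does. Section 7 lists the audit for GP visits and costs, and GP-record coverage may be incomplete where comparison GPs decline.
- If no source captures paper plans, use the GP-recorded care plan outcome already listed (GPMP and TCA, section 4.4 endpoint 5 and Table 9) as the plan-based effect.
- Report online-plan completion only as uptake or fidelity in the intervention arm, and state that it does not satisfy the condition that effectiveness has been shown.

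The cost is a wording change in two places and a check of the data source. The plan-based ratio may look less favourable.
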